### 7.1 Sample Size

Approximately 800 treated patients

[Rationale for the sample size]

The sample size estimation is based on the number of subjects who have completed the preceding study of ASP015K (Study 015K-CL-RAJ1) and participate in this extension study (201 subjects), the planned number of subjects in Study 015K-CL-RAJ3 excluding those in the reference group (300 subjects), and the planned number of subjects in Study 015K-CL-RAJ4 (510 subjects).

### 7.2 Analysis Set

The study analyses will be performed on the following analysis sets. Final judgments on inclusion/exclusion of subjects from the analyses will be made following case reviews based on the opinions and advice from a medical expert.

#### 7.2.1 Full Analysis Set (FAS)

The FAS is defined as all subjects who receive at least one dose of study drug and have measurements for any of the efficacy endpoints.

#### 7.2.2 Safety Analysis Set (SAF)

The SAF is defined as all subjects who received at least one dose of the study drug.

- CONFIDENTIAL -

### **7.2.3 Pharmacodynamics Analysis Set (PDAS)**

The PDAS is defined as all subjects who receive at least one dose of the study drug and from whom a pharmacodynamics sample is collected at one or more points of time.

## **7.3 Demographics and Other Baseline Characteristics**

Demographics and other baseline characteristics will be summarized for the SAF. Descriptive statistics will include sample size, mean, standard deviation, minimum, median and maximum for continuous variables, and frequency and percentage for categorical variables. Unless otherwise specified, data will be tallied by each preceding study (RAJ1, RAJ3, and RAJ4) and for the entire population of RAJ2. When needed, analyses will take into consideration the treatment groups in the preceding studies as well as the regions (i.e. Japan, Korea, and Taiwan).

## **7.4 Analysis of Efficacy**

Efficacy analysis will be conducted on the FAS. The efficacy results will be summarized with sample size, mean, standard deviation, minimum, median and maximum by time point for continuous variables, and frequency and percentage for categorical variables. Subgroup analyses for sex and age categories may be explored. Unless otherwise specified, data will be tallied by each preceding study (RAJ1, RAJ3, and RAJ4) and for the entire population of RAJ2. When needed, analyses will take into consideration the treatment groups in the preceding studies as well as the regions (i.e. Japan, Korea, and Taiwan).

## **7.5 Analysis of Safety**

Unless otherwise specified, data will be tallied by each preceding study (RAJ1, RAJ3, and RAJ4). When needed, analyses will take into consideration the treatment groups in the preceding studies as well as the regions (i.e. Japan, Korea, and Taiwan).

### **7.5.1 Adverse Events**

AEs will be coded using the MedDRA. The incidence of AEs, SAEs, AEs leading to treatment discontinuation, and AEs whose relationship to the study drugs could not be ruled out will be summarized by system organ class and preferred term. The incidence of AEs by severity will also be summarized. All AEs will be listed.

### **7.5.2 Laboratory Measurements**

Descriptive statistics will be used to summarize clinical laboratory measurements and change from baseline if quantitative, by time point. Laboratory data will be displayed in listings.

- CONFIDENTIAL -

### **7.5.3 Vital Signs**

Descriptive statistics will be used to summarize vital sign measurements and change from baseline by time point.

### **7.5.4 12-lead ECG**

The frequency of each category of 12-lead ECG results will be summarized by time point.

### **7.5.5 Body Weight**

Descriptive statistics will be used to summarize the body weight measurements by time point.

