## 2.3 Variables

### 2.3.1 Safety Variables

- AEs
- Vital signs (body temperature, pulse and blood pressure in sitting position)
- Body weight
- 12-lead ECG
- Chest radiography
- Laboratory assessments

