#### **5.4.7 Radiography**

Chest radiography will be obtained at the study visits every 48 weeks from Week 0 onward according to Table 1, Schedule of Assessments, as well as at end of treatment/early termination. However, chest radiography at end of treatment/early termination need not be performed if data obtained within 24 weeks prior to the end of treatment/early termination are available. The investigator or sub-investigator will read the chest radiographs, assess the result as “normal,” “abnormal but not to a clinically significant degree,” or “clinically significant abnormality” and record the results of the assessment in the CRF. If the finding is “abnormal but not to a clinically significant degree” or “clinically significant abnormality,” the finding will be recorded in the CRF.

- CONFIDENTIAL -

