## (3) 12-lead ECG, Chest Radiography

Time points defined in analysis	Reference date*	Acceptable time range
Week 0**	Day 1	Day 1
Week 48	Day 337	Day 330 to Day 344
Week 96	Day 673	Day 659 to Day 687
Week 96 + 48 × x	$\text{Day } 7 \times (96 + 48 \times x) + 1$	$\text{Day } 7 \times (96 + 48 \times x) - 13$ to Day $7 \times (96 + 48 \times x) + 15$
End/discontinuation of treatment***	Day of the last dose	Day 2 to 2 days after the last dose

\*: Day 1 represents the first day of study treatment.

\*\*: Regarding chest radiography, it is allowed to use data obtained within 28 days prior to the Week 0 visit.

\*\*\*: Chest radiography at the end/discontinuation of treatment is unnecessary if one has been taken within 24 weeks from the day of discontinuation.

- CONFIDENTIAL -

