6.2 Safety Variables

- AEs
- Vital signs (body temperature, pulse rate and blood pressure in sitting position)
- Body weight
- 12-lead ECG
- Chest radiography
- Laboratory assessments

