7.5.4 Electrocardiograms (ECGs)

<12-lead ECG>

• Raw values (categorical) and changes from Week 0 (shift from Week 0) will be summarized, and the summaries will include number and percentage of subjects with normal, not clinically significant abnormal and clinically significant abnormal 12 lead ECG findings.

^(*) Combination of values measured within same sample

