7.5.5 Chest radiography

Chest radiography will be provided as a subject listing only.

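### Chest radiographs go to a listing with no planned count of new abnormalities since Week 0, and body weight is planned as raw values only and has no post-baseline analysis in the SAP

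*Protocol*

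**What the plan says.** Protocol 2.3.1 and SAP 6.2 each name six safety variables. "Chest radiography" and body weight are separate items in both lists. The SAP defines vital signs as "Vital signs (body temperature, pulse rate and blood pressure in sitting position", so weight is not part of them.

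**Chest radiography.** Protocol 5.4.7 schedules films every 48 weeks from Week 0 and at end of treatment. That last film is waived if one was taken in the preceding 24 weeks. The section says "The investigator or sub-investigator will read the chest radiographs, assess the result as" one of three grades: normal, abnormal without clinical significance, or clinically significant. Protocol 5.4.6 grades the ECG the same way. The two share one table of time points in Protocol 7.8.3 and again in SAP 7.11.6. On the Week 0 film the Protocol table adds: "Regarding chest radiography, it is allowed to use data obtained within 28 days prior to the Week 0 visit". Protocol 7.5 has no subsection on chest radiography, and SAP 7.5.5 reads: "Chest radiography will be provided as a subject listing only". For ECG, SAP 7.5.4 reads: "Raw values (categorical) and changes from Week 0 (shift from Week 0) will be summarized".

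**Body weight.** Protocol 7.5.5 reads: "Descriptive statistics will be used to summarize the body weight measurements by time point". The corresponding sentence for vital signs, in Protocol 7.5.3, is: "Descriptive statistics will be used to summarize vital sign measurements and change from baseline by time point". SAP 7.11.6 sets windows for weight from Week 0 through Week 132 and every 12 weeks after that, plus end of treatment and follow-up. SAP 7.5 has no weight subsection and Appendix 3 has no weight row. The SAP uses weight only at Week 0, as a demographic variable (7.2.2.1) and as a subgroup factor (7.5.1 and 7.8.1).

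**The concern.** The study's stated aim is long-term safety and efficacy. The drug is an immunosuppressant, and Protocol 1.4 draws attention to tuberculosis, pneumonitis and malignancy reported with another drug of its class. Chest films are the scheduled imaging that bears on those risks. The films are collected, graded and assigned to time points, yet no table says how many subjects had a film worse than their Week 0 film. The plan gives no reason for treating two identically graded tests differently.

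For weight, the exposure categories in SAP 7.3.1 run past 84 months, and SAP 7.5.1.2 itself recognises differing durations and possible differential dropout. Over that span, a trend in raw visit means can come from who is still in the study as much as from anyone gaining or losing weight. The SAP is meant to elaborate the protocol analysis, but it leaves out even the raw summary that the Protocol commits to.

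**Working it through.** The plan states no figure to reproduce. The check is to follow each of the six safety variables in SAP 6.2 to its planned output after Week 0.

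| Safety variable | Protocol 7.5 | SAP 7.5 and Appendix 3 |
|---|---|---|
| Adverse events | Incidence tables | Occurrence and per-100-patient-year tables |
| Laboratory tests | By time point, with change | By visit, change and shift from Week 0 |
| Vital signs | By time point, with change | By visit, with change from Week 0 |
| 12-lead ECG | Category frequencies by time point | Category frequencies and shift from Week 0 |
| Chest radiography | No subsection | Listing; no Appendix 3 row |
| Body weight | Raw values by time point | No subsection; no Appendix 3 row |

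Tally for the SAP: 4 of 6 have a planned post-baseline summary, 1 has a listing, and 1 has nothing after Week 0 (4 + 1 + 1 = 6).

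**Which films exist.** A shift table needs a Week 0 film and a later one.
- A Week 0 film is required of everyone, with the 28-day allowance.
- Under the current schedule, later films fall at Weeks 48, 96 and 96 + 48x, and at end of treatment unless waived.
- Subjects from RAJ1 (201 in the sample-size rationale) began under protocol version 1.3. Its schedule, in Protocol Appendix 7, has a film at Week 0 and afterwards only if clinically indicated. Their visits under that version therefore have no scheduled post-baseline film.
- SAP 7.11.6 adds 24-week films in Taiwan only.

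A shift table is feasible, but its denominator is smaller than the safety analysis set.

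**Why raw visit means mislead.** Let A be the mean Week 0 weight of all subjects and S the mean Week 0 weight of those still measured at visit t. Let M be their mean weight at visit t. Then

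M − A = (M − S) + (S − A).

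The first bracket is the mean within-subject change among those still measured. The second is pure composition. If a share d is no longer measured, and those subjects had mean Week 0 weight L, then A = (1 − d)S + dL, so S − A = d(S − L). This term is nonzero whenever leavers and stayers differed in weight at Week 0, even if no subject's weight changes. A table of raw means shows only M − A. A change-from-Week-0 table shows M − S directly.

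The documents give no weights, dropout shares or standard deviations for this study, so no size in kilograms is claimed.

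**The case against.** The strongest reply on chest films is the adverse-event route. Under Protocol 5.5.1 a test abnormality that the investigator considers clinically significant is an adverse event. A film newly graded that way should therefore reach the tables by system organ class and preferred term and the per-100-patient-year rates. Serious infections, malignancies and infections needing intravenous treatment have dedicated outputs in SAP 7.5.1, with confidence intervals. Those diagnoses matter more than a three-level local reading. This stands. What those tables lack is each subject's Week 0 film status, a denominator of films read, and abnormal films judged not clinically significant. Protocol 5.5.1 names ECG data among its examples, and ECG still gets both tables.

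On weight, Protocol 7.5.5 still commits to descriptive statistics by time point, and nothing in the SAP withdraws it. Protocol Section 7 and SAP 7.1 set Week 0 as the safety baseline, and SAP 7.1 defines how change is calculated. These rules do not order a weight table. SAP 7.1 leaves table formats to a separate specification that is not available here. A weight table may appear there, but the SAP would still not have planned it.

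A reader might infer that the two variables have no usable analysis, or that movement from a normal to an abnormal film could not be determined. The documents do not support either inference. The Protocol weight summary stands, Week 0 weight is summarised, and film grades are recorded and listed, so shifts could be tallied by hand. Nor does the listing contradict the Protocol, which plans no chest-film analysis.

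**Conclusion.** The point holds as a gap in planned summaries for two of six safety variables. Chest radiography has ECG's categories and time points but no planned count of new abnormalities from Week 0. Body weight has SAP windows but no post-baseline SAP analysis, and the Protocol plans raw values without change from Week 0.

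The consequence is modest. The study is open-label, and its planned summaries are descriptive. No test, sample size or error rate is touched, and the main infection and malignancy evidence comes from the adverse-event tables. Nothing in the documents shows that a conclusion would change. The weight argument rests on one assumption: that subjects who leave may differ in Week 0 weight from those who stay. The direction and amount are unknown. Change from Week 0 removes that composition term. It still describes only the subjects who remain, so it does not cure dropout related to weight change itself.

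**What to change.** **Chest radiography (SAP 7.5.5 and Appendix 3).** Add frequency by category and shift from Week 0 at the time points common to all regions (Weeks 48, 96 and 96 + 48x) and at end of treatment where a film exists. Use as denominator the subjects with both a Week 0 film and a post-baseline film, and print that number in each column. The reasons are the waiver of the end-of-treatment film and the absence of scheduled post-baseline films for RAJ1 subjects under version 1.3. State whether an earlier film may fill the end-of-treatment column under the carry-forward rule in SAP 7.11.2. Keep the listing, and list Taiwan's additional 24-week films there.

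**Body weight (Protocol 7.5.5, SAP 7.5.3 and Appendix 3).** Add raw value and change from Week 0 by visit, by preceding study and overall, with the number measured at each visit.

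**Cost.** A few lines of text and a few extra tables modelled on the ECG and vital-sign ones. The ECG layout needs the denominator rule added. No new data are needed. The drawback is chest-film denominators smaller than the full safety analysis set, which the tables should show openly.

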## **7.6 Other Analyses**

Any other analyses, including disposition of subjects, exposure to study drug and etc., will be specified in a statistical analysis plan (SAP).

### **7.6.1 Analysis of Pharmacodynamics**

Analysis of pharmacodynamics will be conducted on the PDAS. Descriptive statistics will be used to summarize the pharmacodynamics measurements and change from baseline by time point. Unless otherwise specified, data will be tallied by each preceding study (RAJ1, RAJ3, and RAJ4) and for the entire population of RAJ2. When needed, analyses will take into consideration the treatment groups in the preceding studies as well as the regions (i.e. Japan, Korea, and Taiwan).

## **7.7 Interim Analysis (and Early Discontinuation of the Clinical Study)**

Not applicable. However, while the study is ongoing, safety data review and evaluation of safety will be performed according to the operating procedures developed separately by the Data and Safety Monitoring Board (DSMB; see Section 10.1).

## **7.8 Handling of Missing Data, Outliers, Visit Windows, and Other Information**

Final judgments on handling of missing data, outliers, visit windows, and other information will be made at the Case Review Meeting based on the opinions and advice from a medical expert prior to data lock and included in the SAP.

The acceptable time ranges of the efficacy and safety examinations, observations, etc. from the date of initial study treatment (Day 1) are defined as follows. If there are multiple data available over the same period of time, the data obtained on the day closest to the reference date will be utilized; the later date will be applied if the number of days from the reference date is equal. Missing data at the end or discontinuation of treatment will be imputed using the LOCF method.

- CONFIDENTIAL -

Since the study period of this study differs depending on the subject, the timing for the required visits to the study center will also differ from subject to subject. Only subjects who transferred from study RAJ1, but not those who transferred from studies RAJ3 or RAJ4, are required to come for visits at Week 2, Week 4, Week 8, Week 16, Week 20, Week 28, Week 32, Week 40, and Week 44. Therefore, these time points defined in the analysis are set only for the subjects from study RAJ1.

### 7.8.1 Handling of Schedule of Assessments of Efficacy Variables

For data obtained after the end of treatment, the data obtained within +2 days after the last dose will be included in analysis, except for the data at the end of the study (at time of follow-up).

- (1) RA disease activity (TJC, SJC, PGA, SGA, subject's assessment of pain), CRP, ESR

Time points defined in analysis	Reference date*	Acceptable time range
Week 0	Day 1	Day 1
Week 2	Day 15	Day 12 to Day 18
Week 4	Day 29	Day 22 to Day 36
Week 8	Day 57	Day 50 to Day 64
Week 12	Day 85	Day 78 to Day 92
Week 16	Day 113	Day 106 to Day 120
Week 20	Day 141	Day 134 to Day 148
Week 24	Day 169	Day 162 to Day 176
Week 28	Day 197	Day 190 to Day 204
Week 32	Day 225	Day 218 to Day 232
Week 36	Day 253	Day 246 to Day 260
Week 40	Day 281	Day 274 to Day 288
Week 44	Day 309	Day 302 to Day 316
Week 48	Day 337	Day 330 to Day 344
Week 60	Day 421	Day 407 to Day 435
Week 72	Day 505	Day 491 to Day 519
Week 84	Day 589	Day 575 to Day 603
Week 96	Day 673	Day 659 to Day 687
Week 108	Day 757	Day 743 to Day 771
Week 120	Day 841	Day 827 to Day 855
Week 132	Day 925	Day 911 to Day 939
Week 132 + 12 × x	Day $7 \times (132 + 12 \times x) + 1$	Day $7 \times (132 + 12 \times x) - 13$ to Day $7 \times (132 + 12 \times x) + 15$
End/discontinuation of treatment	Day of the last dose	Day 2 to 2 days after the last dose
End of the study (at time of follow-up)	28 days after the last dose	21 to 35 days after the last dose

\*: Day 1 represents the first day of study treatment.

- CONFIDENTIAL -

## (2) Patient Questionnaires (HAQ-DI, FACIT-Fatigue)

The schedule for FACIT-Fatigue applies only to subjects who transferred from study RAJ1.

Time points defined in analysis	Reference date*	Acceptable time range
Week 0	Day 1	Day 1
Week 2	Day 15	Day 12 to Day 18
Week 4	Day 29	Day 22 to Day 36
Week 8	Day 57	Day 50 to Day 64
Week 12	Day 85	Day 78 to Day 92
Week 16	Day 113	Day 106 to Day 120
Week 20	Day 141	Day 134 to Day 148
Week 24	Day 169	Day 162 to Day 176
Week 28	Day 197	Day 190 to Day 204
Week 32	Day 225	Day 218 to Day 232
Week 36	Day 253	Day 246 to Day 260
Week 40	Day 281	Day 274 to Day 288
Week 44	Day 309	Day 302 to Day 316
Week 48	Day 337	Day 330 to Day 344
Week 60	Day 421	Day 407 to Day 435
Week 72	Day 505	Day 491 to Day 519
Week 84	Day 589	Day 575 to Day 603
Week 96	Day 673	Day 659 to Day 687
Week 108	Day 757	Day 743 to Day 771
Week 120	Day 841	Day 827 to Day 855
Week 132	Day 925	Day 911 to Day 939
Week 132 + 12 × x	$\text{Day } 7 \times (132 + 12 \times x) + 1$	Day 7 × (132 + 12 × x) – 13 to Day 7 × (132 + 12 × x) + 15
End/discontinuation of treatment	Day of the last dose	Day 2 to 2 days after the last dose
End of the study (at time of follow-up)**	28 days after the last dose	21 to 35 days after the last dose

\*: Day 1 represents the first day of study treatment.

\*\* : The assessment at the end of the study (at the time of follow-up) will be scheduled only for HAQ-DI.

- CONFIDENTIAL -

(3) Patient Questionnaires (SF-36v2®)

Time points defined in analysis	Reference date*	Acceptable time range
Week 0	Day 1	Day 1
Week 4**	Day 29	Day 22 to Day 36
Week 8**	Day 57	Day 50 to Day 64
Week 12**	Day 85	Day 78 to Day 92
Week 16**	Day 113	Day 106 to Day 120
Week 20**	Day 141	Day 134 to Day 148
Week 24	Day 169	Day 162 to Day 176
Week 28**	Day 197	Day 190 to Day 204
Week 32**	Day 225	Day 218 to Day 232
Week 36**	Day 253	Day 246 to Day 260
Week 40**	Day 281	Day 274 to Day 288
Week 44**	Day 309	Day 302 to Day 316
Week 48	Day 337	Day 330 to Day 344
Week 60**	Day 421	Day 407 to Day 435
Week 72	Day 505	Day 491 to Day 519
Week 84**	Day 589	Day 575 to Day 603
Week 96	Day 673	Day 659 to Day 687
Week 108**	Day 757	Day 743 to Day 771
Week 120	Day 841	Day 827 to Day 855
Week 120 + 12 × x**	$\text{Day } 7 \times (120 + 12 \times x) + 1$	$\text{Day } 7 \times (120 + 12 \times x) - 13$ to $\text{Day } 7 \times (120 + 12 \times x) + 15$
End/discontinuation of treatment	Day of the last dose	Day 2 to 2 days after the last dose

\*: Day 1 represents the first day of study treatment.

\*\*: Scheduled only for subjects who transferred from study RAJ1. For subjects who transferred from studies RAJ3 or RAJ4, the survey is administered every 24 weeks after Week 120. Starting at the first visit after the revision of the study protocol, the survey will be administered to subjects who transferred from study RAJ1 also every 24 weeks.

## (4) Patient Questionnaires (WPAI [subjects from RAJ3 or RAJ4])

Scheduled only for subjects who transferred from studies RAJ3 or RAJ4.

Time points defined in analysis	Reference date*	Acceptable time range
Week 0	Day 1	Day 1
Week 24	Day 169	Day 162 to Day 176
Week 48	Day 337	Day 330 to Day 344
Week 72	Day 505	Day 491 to Day 519
Week 96	Day 673	Day 659 to Day 687
Week 120	Day 841	Day 827 to Day 855
Week 120 + 24 × x	$\text{Day } 7 \times (120 + 24 \times x) + 1$	$\text{Day } 7 \times (120 + 24 \times x) - 13$ to $\text{Day } 7 \times (120 + 24 \times x) + 15$
End/discontinuation of treatment	Day of the last dose	Day 2 to 2 days after the last dose

\*: Day 1 represents the first day of study treatment.

- CONFIDENTIAL -

### 7.8.2 Handling of Schedule of Assessments of Pharmacodynamics Variables

For data obtained after the end of study treatment, the data obtained within +2 days after the last dose will be included in analysis, except for the data at the end of the study (at time of follow-up).

#### (1) Lymphocyte subsets

Time points defined in analysis	Reference date*	Acceptable time range
Week 0	Day 1	Day 1
Week 48	Day 337	Day 330 to Day 344
Week 96	Day 673	Day 659 to Day 687
Week $96 + 48 \times x$	Day $7 \times (96 + 48 \times x) + 1$	Day $7 \times (96 + 48 \times x) - 13$ to Day $7 \times (96 + 48 \times x) + 15$
End/discontinuation of treatment	Day of the last dose	Day 2 to 2 days after the last dose
End of the study (at time of follow-up)	28 days after the last dose	21 to 35 days after the last dose

\*: Day 1 represents the first day of study treatment.

### 7.8.3 Handling of Schedule of Assessments of Safety Variables

For data obtained after the end of study treatment, the data obtained within +2 days after the last dose will be included in analysis, except for the data at the end of the study (at time of follow-up).

- CONFIDENTIAL -

